#### 11. STATISTICAL CONSIDERATIONS

This is a pilot study for which the initial aim was to accrue 20 paediatric patients with bMMRD tumours. Following amendment, the study inclusion criteria will be expanded to include those with hypermutant tumours (as determined by estimation of TMB by targeted gene sequencing), as well as those with CMMRD, including bMMRD tumours, and consequently the total enrollment will be increased to 50 patients.

The primary objective is to determine the ORR as well as to estimate the efficacy of nivolumab in patients with hypermutant tumours. The study is predicated on the hypothesis that patients with hypermutated tumours will derive greater benefit from nivolumab than those without; however, the relevant threshold of TMB is not yet established. Consequently, in this pilot study, patients will be recruited into two cohorts depending on TMB. This will provide the opportunity to treat patients with a relatively low TMB ( $\geq$ 5 to <10/Mb, estimated ~15% of tumors) to assess for responses to nivolumab, while a separate cohort for patients with TMB ( $\geq$ 10/Mb, estimated ~5% of tumors) will ensure that overall study enrollment is not dominated by patients with lower TMB.

A Simon two-stage design will be used within each cohort.

For cohort A (TMB ( $\geq$ 5 to <10/Mb), the null hypothesis that the true response rate is only 10% will be tested against a one-sided alternative. In the first stage, 10 patients will be accrued. If there are 1 or fewer responses in these 10 patients, the cohort will be closed. Otherwise, 10 additional patients will be accrued for a total of 20. The null hypothesis will be rejected if 5 or more responses are observed in 20 patients. This design yields a type I error rate of 0.05 and power of 85% when the true response rate is 35%. Accrual to this cohort will stop if evidence accumulates that the efficacy is lower than the specified acceptable levels. If five or more ( $\geq$ 5) patients experience objective responses (CR+PR), then we will conclude that Nivolumab is sufficiently active in patients with TMB  $\geq$ 5 to <10/Mb to warrant recommendation for continued investigation.

For Cohort B (TMB  $\geq$ 10/Mb), in the first stage, 10 patients will be accrued. If there are 1 or fewer responses in these 10 patients, the cohort will be closed. Otherwise, 20 additional patients will be accrued for a total of 30. The null hypothesis will be rejected if 6 or more responses are observed in 30 patients. This design yields a type I error rate of 0.05 and power of 80% when the true response rate is 30%. Accrual to this cohort will stop if evidence accumulates that the efficacy is lower than the specified acceptable levels. If six or more ( $\geq$ 6) patients experience objective

responses (CR+PR), then we will conclude that Nivolumab is sufficiently active in patients with  $TMB \ge 10/Mb$  to warrant recommendation for continued investigation.

Patients already recruited to study at the time of amendment will be retrospectively allocated to the appropriate cohort based on TMB. It is anticipated that most of these patients with CMMRD will have TMB ≥10/Mb and will therefore fall into cohort B. Any patients with CMMRD for whom TMB is not available will be analyzed separately in Cohort C.

In order to make decisions about further exploring the use of nivolumab in this patient population, a likelihood Bayesian analysis will also be used to provide estimates of likely effect sizes based on results from this pilot study. Posterior probability distributions for response rate will be plotted, using non-informative priors.

For example, in Cohort A, a response in 5 of 20 patients (estimate response rate 0.25), indicates a probability that the true RR is >0.2 of 0.77; while there is only a 0.01 probability that the true RR is <0.1. Similarly, for Cohort B, a response in 6 of 30 patients (estimated RR 0.2), indicates a probability that the true RR is >0.2 of 0.57; while there is a 0.03 probability that the true RR is <0.1.

Patients who are evaluable for objective response are those who meet the definition as per *Section 10.2.1.2*.

All enrolled patients who received at least one dose of any study drug will be evaluable for safety. A safety evaluation will be performed by the Safety Committee after Patient 1 Cycle 1, Patient 4 Cycle 1, Patient 7 Cycle 1, and Patient 10 Cycle 1. Enrollment will be held after each time point until a safety evaluation of adverse events and serious adverse events confirms it is safe to resume enrollment.

Any deviation from this statistics section of the protocol along with the accounting for missing, unused and spurious data will be described in the final report.

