Sample Size:	50 patients with hypermutant refractory or recurrent tumours across all					
Sample Size.	diagnoses will be recruited, including those with RRD, such as CMMRD.					
	Nivolumab (also referred to as Opdivo® or BMS-936558 or MDX1106) is					
	a human monoclonal antibody (HuMAb; immunoglobulin G4 [IgG4]-					
	S228P) that targets and inhibits the programmed death-1 (PD-1) cluster of					
	differentiation 279 (CD279) cell surface membrane receptor.					
Investigational  Products	Regimen: Nivolumab will be administered every 14 days until confirmed					
Product:	disease progression or treatment discontinuation due to unacceptable					
	toxicities. Treatment may extend up to 2 years in patients who show					
	clinical and radiological benefit.					

	Dose: 3 mg/kg intravenously (IV) as a continuous infusion over 60 min (+/-10 min window).  This is an open-label, single arm, multi-center, pilot study of nivolumab in paediatric patients with recurrent or refractory hypermutant malignancies aged 12 months to <25 years of age. Local centres are only obligated to treat/admit patients in accordance their age range capabilities.  The purpose of this study is to assess response of treatment with nivolumab in children with hypermutated cancers, including those with RRD, such as CMMRD syndrome.  This study will be performed in two parts: Part I – Molecular Profiling and Part II – Treatment and Companion Biomarker Studies.  In order to participate in Part I, patient's cancer specimen must undergo a
Overview of Study Design:	gene sequencing panel to determine TMB or else have proof of RRD (for those patients for whom it is not possible to obtain a TMB level). Once TMB or proof of RRD is established, and Part II eligibility is confirmed, patients will be stratified into cohorts based on levels of TMB or RRD status (as outlined below).
	The TMB assay must be performed in a Study Chair or Co-chair specified, CLIA-certified laboratory. Proof of RRD status may be established by assays performed in either a CLIA or ISO 15189-certified laboratory in accordance with local regulations and at the discretion of the Study Chair or Co-chair.
	Part I - Molecular Profiling

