### Part II - Treatment and Companion Biomarker Studies

Patients with cancers that have been confirmed as hypermutant based on a report by a specific-TMB assay (acquired via **Part I** participation or previously) or have proof of RRD will be consented and enrolled into to **Part II**.

Cohort stratification of patients enrolled in **Part II** is based on their identified TMB levels or RRD status:

- Cohort A: TMB  $\geq$ 5 but <10 mutations/Mb (max. 20 patients);
- Cohort B: TMB  $\geq$ 10 mutations /Mb (max. 30 patients);
- Cohort C: unobtainable TMB in a patient with RRD.

N.B.: Patients stratified to Cohort C will be reallocated to Cohorts A or B if a TMB value subsequently becomes available.

All eligible patients will receive nivolumab intravenously (IV) at a dose of 3mg/kg administered every 14 days (two weeks). Two doses comprise one cycle (28 days or four weeks). Evaluations will be performed according to the schedule provided. Samples to perform 'Companion Biomarkers' research to further our understanding of paediatric hypermutant cancer response to nivolumab will be obtained (see *Lab Manual* for details).

N.B: We strongly recommend that all patients with confirmed or suspected RRD syndromes undergo screening for possible concurrent malignancies (see Section 8.0).

Patients will be monitored for toxicity using standard National Cancer Institute Common Terminology Criteria for Adverse Events (NCI CTCAE), version 4.03. Response assessment will use iRECIST criteria for solid tumours (modified for neuroblastoma using the revised INRC), iRANO criteria for CNS malignancies, RECIL 2017 criteria for lymphomas, revised criteria according to Creutzig, et al. (2012) for acute myeloid leukemia (AML; see *Section 10.13*), and criteria as specified in *Section 10.14* for acute lymphoblastic leukemia (ALL).

The Safety visit will be completed when the patient comes off treatment and prior to entering the Follow-Up Period.

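### Cohort B's type I error is 0.0525 rather than 0.05 at a 10% null that is written only for Cohort A, and Cohort C has no stated place in the total of 50

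*Protocol*

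**What the plan says.** Section 11 (Statistical Considerations), repeated under Statistical Methods in the synopsis, states: "A Simon two-stage design will be used within each cohort".

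- **Cohort A** (TMB from 5 to below 10/Mb): "the null hypothesis that the true response rate is only 10% will be tested against a one-sided alternative". The cohort closes at 1 or fewer responses in the first 10 patients. On continuing, the text reads: "Otherwise, 10 additional patients will be accrued for a total of 20". The final decision rule is then given as: "The null hypothesis will be rejected if 5 or more responses are observed in 20 patients". The claimed properties are: "This design yields a type I error rate of 0.05 and power of 85% when the true response rate is 35" per cent.
- **Cohort B** (TMB of 10/Mb or more): the stage 1 rule is the same, 20 further patients make 30, and the null is rejected at 6 or more responses. The claim is: "This design yields a type I error rate of 0.05 and power of 80% when the true response rate is 30" per cent. This paragraph refers to a null hypothesis but gives no rate for it.

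The synopsis sets the sample size at "50 patients with hypermutant refractory or recurrent tumours across all" diagnoses. Section 3.1.1 gives maxima of 20 for Cohort A and 30 for Cohort B. It defines Cohort C as "unobtainable TMB in a patient with RRD", with no maximum or expected number. Cohort C patients are treated in Part II and analysed separately, and they move to A or B if a TMB value is later obtained.

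**The concern.** A type I error rate has meaning only against a stated null. Cohort B's null must be inferred, and at the value that a reader would infer, the quoted 0.05 is passed rather than met. A final report that repeats 0.05 as the error bound for Cohort B would understate it a little.

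The second matter is one of counting. The maxima for A and B add up to the whole planned enrolment, yet a third group also receives treatment. The protocol does not say whether that group counts toward the 50. If it does, and both A and B continue to stage 2, Cohort C patients would take places that the A and B calculations rely on.

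**Working it through.** **Inputs (Section 11).** Both cohorts: n1 = 10, close at 1 or fewer responses. Cohort A: n = 20, reject at 5 or more, null 10%, alternative 35%. Cohort B: n = 30, reject at 6 or more, alternative 30%. Null for Cohort B: **assumed 10%**, carried over from Cohort A. The Cohort B Bayesian example, which uses 0.1 as its lower benchmark, supports this.

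**Formula.** With X1 ~ Bin(10, p) and X2 ~ Bin(n − 10, p), and c the rejection cut-off:

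P(reject) = Σ over x from 2 to 10 of P(X1 = x) × P(X2 ≥ c − x)

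**Cohort B, n = 30, c = 6, p = 0.10**

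| x | P(X1 = x) | P(X2 ≥ 6 − x) | product |
|---|---|---|---|
| 2 | 0.19371 | 0.13295 | 0.02575 |
| 3 | 0.05740 | 0.32307 | 0.01854 |
| 4 | 0.01116 | 0.60825 | 0.00679 |
| 5 | 0.00149 | 0.87842 | 0.00131 |
| 6 or more | 0.00015 | 1 | 0.00015 |

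Sum: **0.0525** (stated: 0.05).

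**Cohort B power, p = 0.30.** The same five terms are 0.20847 + 0.25736 + 0.19859 + 0.10284 + 0.04735 = **0.815** (stated: 80%).

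**Dependence on the unstated null.** For the same rule the type I error is 0.0342 at a null of 9%, 0.0485 at 9.8%, 0.0525 at 10% and 0.217 at 15%. The stated 0.05 is met only for a null a little below 10%.

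**Alternatives for Cohort B, null 10%, alternative 30%**

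| Design | Type I error | Power |
|---|---|---|
| 1/10, then 6 or more of 30 (protocol) | 0.0525 | 81.5% |
| 1/10, then 6 or more of 29 | 0.0471 | 80.5% |
| 1/10, then 6 or more of 28 | 0.0418 | 79.3% |
| 1/10, then 7 or more of 30 | 0.0206 | 75.9% |

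A search over two-stage designs for these targets (error at most 0.05, power at least 80%) gives the 29-patient row as the Simon optimal design.

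**Cohort A.** Type I error at 10%: 0.0376 (stated 0.05). Power at 35%: 0.129704 + 0.230541 + 0.234470 + 0.153570 + 0.094934 = 0.8432, or 84.3% (stated 85%).

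**Total.** 20 + 30 = 50, so 50 − 50 = 0 places remain for Cohort C if A and B both fill.

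**Illustration only.** If five Cohort C patients were counted against Cohort B (30 − 5 = 25, cut-off still 6), Cohort B's power at 30% would be 74.0%. Five is an assumption; with three (27 patients) it would be 77.9%.

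**The case against.** The protocol gives the error rate to two decimals, and 0.0525 rounds to 0.05. Cohort B's power is met. This is a pilot whose positive outcome is only a recommendation to investigate further, and a Bayesian analysis stands beside the test; its worked examples reproduce under a uniform prior. The null of 10% follows naturally from the preceding Cohort A paragraph. Thirty patients is a legitimate choice, and 29 is a preference. All of this stands as to size. It does not remove the facts that the nominal level is passed when read as a ceiling and that a primary null hypothesis is left unwritten.

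A reader might also infer that Cohort A's figures are wrong. They are not wrong in a way that matters: 0.0376 lies inside 0.05, as is usual for a discrete test, and 84.3% is within one point of 85%.

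On Cohort C, a reader might infer that either enrolment must exceed 50 or A and B cannot finish. The documents do not support that. Twenty and thirty are maxima; a cohort with a true response rate of 10% closes after 10 patients with probability 0.74, freeing places; and Cohort C is a residual group whose patients leave it once a TMB value exists. It also carries no hypothesis test and so needs no powered size. What stands is that the protocol does not say whether Cohort C counts.

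**Conclusion.** The point holds in a limited form. At a 10% null, Cohort B's type I error is 0.0525 against a stated 0.05, an excess of 0.0025. Its power of 81.5% supports the stated 80%. The result rests on the 10% null, which the protocol states for Cohort A alone, and that omission is part of the finding. Neither the decision rule nor the trial's conclusions are undermined. Cohort A needs at most a change of wording.

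The Cohort C gap is real but conditional: it matters only if A and B both pass stage 1. It would be tempting to report that Cohort B's power falls to 74%. The protocol gives no Cohort C number and does not say that such places would come from Cohort B, so that figure is illustrative and not a property of the design.

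**What to change.** In Section 11 and in the synopsis:

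1. State the null response rate of 10% for Cohort B.
2. Then choose one of two options. Either keep 30 patients and give the type I error as 0.053 and power as 81%, or set the second stage to 19 patients (10 + 19 = 29) with the same cut-offs and give 0.047 and 80.5%. The second option also changes the Cohort B maximum, the A + B total (20 + 29 = 49) and the 6-of-30 Bayesian example.
3. In the same edit, give Cohort A as 0.038 and 84%.
4. State that Cohort C is additional to the 50, so that it cannot displace Cohort A or B patients if both reach stage 2.

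The cost is a few sentences. Cohort B loses one patient at most, or its stated error rate becomes slightly less favourable. Counting Cohort C outside the 50 means that total treated enrolment may exceed 50 by however many patients remain in it.

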## 4.2.2 Part II - Treatment and Companion Biomarker Inclusion Criteria

In order to participate in **Part II**, patients must meet the following criteria:

- **1. Consent/ Assent:** Patient and Legally Acceptable Representative (LAR; such as a parent or guardian, as applicable) must be willing and able to provide written informed consent/assent for the trial as per local requirements.
- **2. Confirmation of Hypermutation or Proof of RRD:** patient must have completed and verified a sufficient TMB level or have proof of RRD diagnosed in the appropriate lab, as outlined in the *Lab Manual*.
- 3. Age: patients must be ≥ 12 months and < 25 years of age at the time of Part II enrollment.

  Local centres are only obligated to treat/ admit patients in accordance their age range capabilities.
- **4. Diagnosis:** patients must have had histologic verification of malignancy at the time of initial diagnosis or at relapse (as specified above). Patients with multiple concurrent and/or sequential neoplasms are eligible, including CNS and haematological malignancies.
- **5. Disease status:** patients must have either measurable or evaluable disease in accordance with criteria as outlined in *Section 10*. Tumour lesions situated in a previously irradiated area are considered measurable if progression has been demonstrated in such lesions.
- **6. Treatment options:** patient's current disease state must be one for which there is no known curative therapy or therapy proven to prolong survival with an acceptable quality of life. Chemotherapy-naïve patients will be eligible in cases where first-line therapy does not include chemotherapy (e.g. surgery alone for management of ependymoma).
- 7. Performance status: Karnofsky  $\geq 50\%$  for patients > 16 years of age or Lansky  $\geq 50$  for patients  $\leq 16$  years of age. Patients who are unable to walk because of paralysis, but who are

up in a wheelchair, will be considered ambulatory for the purpose of assessing the performance score.

- **8. Previous treatment:** patients must have fully recovered from the acute toxic effects of all prior anti-cancer therapy.
  - **a. Myelosuppressive chemotherapy:** at least 21 days after the last dose of myelosuppressive chemotherapy (42 days if prior nitrosourea).

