#### **10.2.1.2** Evaluation for Objective Response

Patients who exhibit objective disease progression prior to the end of cycle 1 will be considered evaluable for response. For all other patients, only those patients who have measurable disease present at baseline, have received at least one cycle of therapy, and have had their disease re-evaluated will be considered evaluable for response, whether it be unequivocal or iUPD, but not iCPD (before iCR, iPR or iSD). Patients who have lesions present at baseline that are evaluable, but do not meet the definitions of measurable disease, have received at least one cycle of therapy, and have had their disease re-evaluated will be considered evaluable for non-target disease. The response assessment is based on the presence, absence, or progression of the lesions (unequivocal or iUPD, but not iCPD, before iCR, iPR or iSD).

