### 10.5 Response Criteria for Patients with Solid Tumours and Evaluable Disease

**Evaluable Disease:** The presence of at least one lesion, with no lesion that can be accurately measured in at least one dimension. Such lesions may be evaluable by nuclear medicine techniques, immunocytochemistry techniques, tumour markers or other reliable measures.

**Complete Response (CR):** Disappearance of all evaluable disease.

Partial Response (PR): Partial responses cannot be determined in patients with evaluable disease

**Stable Disease (SD):** That which does not qualify as Complete Response (CR), Partial Response (PR), or Progressive Disease.

**Unconfirmed progressive disease (iUPD):** The appearance of one or more new lesions or evidence of laboratory, clinical, or radiographic progression. iUPD must be assessed between four to eight weeks to confirm progression and become iCPD.

**Confirmed progressive disease (iCPD):** iUPD must be assessed between four to eight weeks to confirm progression and be deemed as iCPD.

**Progressive Disease (PD):** The appearance of one or more new lesions or evidence of laboratory, clinical, or radiographic progression if the next imaging assessment, conducted at least four (4) weeks, but not more than eight (8) weeks after iUPD confirms further progression from iUPD with either an increase of at least 5 mm in the absolute value of the sum of NLT or an increase (but not necessarily unequivocal increase) in the size of NLNT lesions OR the appearance of additional new lesions.

**Best Overall Response (iBOR):** Each patient will be classified according to his "best response" for the purposes of analysis of treatment effect. Best response is determined as outlined in *Section* 10.4.1 and 11 from a sequence of overall response assessments.

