# 13. PROCEDURES FOR DISCONTINUATION OF A PATIENT FROM INVESTIGATIONAL PRODUCT

## 13.1 Procedures for Withdrawal from Study

Patient / Legally Acceptable Representative (LAR; such as a parent or guardian, as applicable) are at any time free to withdraw from study (study medication and assessments), without prejudice to further treatment (withdrawal of consent). Such patients and/or their legal guardians will always be asked about the reason(s) and the presence of any adverse events. If possible, they will be seen and assessed by an investigator. Adverse events will be followed up.

Withdrawn patients who meet the criteria to be evaluable for objective response or non-target response as per *Section 10.2.1.2* will not be replaced. Patients who withdraw from the study prior to meeting the criteria to be evaluable in *Section 10.2.1.2* will be replaced on study.

If a patient does not return for a scheduled visit, every effort should be made to contact the patient and/or their legal guardians. In any circumstance, every effort should be made to document patient outcome and reason for withdrawal, if possible. The investigator should request the patient return for a final visit, if applicable and follow-up with the patient regarding any unresolved adverse events.

If the patient and/or their legal guardians withdraw from the trial and also withdraw consent for disclosure of future information, no further evaluations should be performed, and no additional data should be collected. The Study Chair or Co-Chair may retain and continue to use any data collected before such withdrawal of consent.

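### Section 11 ties objective-response evaluability to a solid-tumour rule requiring measurable disease, although leukaemia and evaluable-only patients are eligible and their responses belong to the primary ORR

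*Protocol*

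**What the plan says.** - **Eligibility (Section 4.2.2).** Criterion 5: "patients must have either measurable or evaluable disease in accordance with criteria as outlined in" Section 10. Criterion 4: "Patients with multiple concurrent and/or sequential neoplasms are eligible, including CNS and haematological malignancies".
- **Primary endpoint (Synopsis, Criteria for Efficacy Evaluation; assessment criteria repeated in Section 3.1.1).** ORR is CR plus PR, judged by iRECIST, revised INRC, iRANO, RECIL 2017, the AML criteria of Section 10.13 and the ALL criteria of Section 10.14.
- **Evaluable-only solid tumours (Section 10.5).** CR is defined. For PR: "Partial responses cannot be determined in patients with evaluable disease".
- **AML (Section 10.13).** PR is defined but expressly left out of the response calculation.
- **Analysis set (Section 11).** "Patients who are evaluable for objective response are those who meet the definition as per" Section 10.2.1.2. No other section is named.
- **Section 10.2.1.2.** It stands under the solid-tumour criteria. Patients who progress before the end of cycle 1 are evaluable, with no measurability condition. For everyone else, "only those patients who have measurable disease present at baseline, have received at least one cycle of therapy, and have had their disease re-evaluated" count as evaluable for response. Evaluable-only patients go to a separate non-target class. Leukaemia is not mentioned.
- **Caps and stages (Sections 3.1.1 and 11).** Cohort A has at most 20 patients and Cohort B at most 30. The stages are described as patients accrued: 10 then 20, and 10 then 30.
- **Replacement (Section 13.1).** "Withdrawn patients who meet the criteria to be evaluable for objective response or non-target response as per" Section 10.2.1.2 are not replaced. Those who withdraw before meeting those criteria are.

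**The concern.** The endpoint definition and the analysis-set definition do not cover the same patients. The endpoint counts leukaemia remissions, and Section 10.5 gives evaluable-only disease a CR. The analysis set, taken at its word, has no route by which either can be scored.

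The rule is also one-sided. The early-progression clause has no measurability condition, so a patient without measurable disease can enter as a failure but not as a responder. That is a fault however few such patients there are.

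At stake are the primary ORR and the go/no-go count in each cohort. The final thresholds are 5 of 20 and 6 of 30, and a cohort closes on 1 or fewer responses in its first 10. If the text stays as it is, someone must decide after responses are known whether a given remission counts.

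**Working it through.** **1. The passages side by side**

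| Patient | Eligible (4.2.2) | Response defined | Scored as responder under Section 11 via 10.2.1.2 | Can enter as early failure | Counts toward cap (3.1.1) |
|---|---|---|---|---|---|
| Measurable solid tumour | yes | CR, PR | yes | yes | yes |
| Evaluable-only solid tumour | yes | CR only (10.5) | no; non-target class | yes | yes |
| ALL | yes | CR, CRp, CRi, PR and cytolytic PR (10.14) | no provision | yes; 10.14 defines progression | yes |
| AML | yes | CR types; PR not counted (10.13) | no provision | unclear; 10.13 defines failure and relapse, not progression | yes |

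**2. The plan's own power**

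Inputs from Section 11: first stage of 10, close on 1 or fewer; reject at 5 or more of 20 (A) or 6 or more of 30 (B); alternatives 35% (A) and 30% (B). The null rate is 10% for A. It is not restated for B and is assumed to be 10%.

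Power = sum over x = 2 to 10 of P(X1 = x) × P(X2 ≥ c − x), with c = 5 or 6, X1 binomial on 10 patients and X2 binomial on the remaining 10 (A) or 20 (B).

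Cohort A at 35%:
- x = 2: 0.1757 × 0.7384 = 0.1297
- x = 3: 0.2522 × 0.9140 = 0.2305
- x = 4: 0.2377 × 0.9865 = 0.2345
- x ≥ 5: 0.2485 × 1 = 0.2485
- total 0.8432, against a stated 85%

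Cohort B at 30% gives 0.8146, against a stated 80%. Exact type I error is 0.038 (A) and 0.053 (B), against a stated 0.05. The design is reproduced.

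**3. Power if a share of capped places cannot be scored**

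The share f is an assumption. Caps and thresholds stay as written. For 10% and 20%, unscorable patients are removed from each stage and the same sum is run on those left. For 5%, which is not a whole number of patients per stage, the response rate is multiplied by 0.95 (A 0.3325, B 0.285).

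| Share f | Scorable patients, A | Power A | Scorable patients, B | Power B |
|---|---|---|---|---|
| 0 | 10 then 20 | 84.3% | 10 then 30 | 81.5% |
| 5% | average-rate method | 80.5% | average-rate method | 77.7% |
| 10% | 9 then 18 | 76.9% | 9 then 27 | 74.2% |
| 20% | 8 then 16 | 66.7% | 8 then 24 | 64.3% |

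Cross-check by the average-rate method: at 10%, A 76.0% and B 73.4%; at 20%, A 65.0% and B 62.8%. A single unscorable patient in the first stage, and none later, gives A 79.6% and B 76.5%.

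**4. The one-sided entry, illustrated**

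Suppose every patient type truly responds at 30%, a share q lacks measurable disease, and a fraction e of those progress before the end of cycle 1. Then apparent ORR = (1 − q) × 0.30 / [(1 − q) + q × e].
- q = 0.20, e = 0.30: 0.24 / 0.86 = 27.9%
- q = 0.20, e = 0.50: 0.24 / 0.90 = 26.7%

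q and e are assumed. The direction of the bias does not depend on their values.

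**The case against.** The strongest reply is that, read as a whole, the protocol intends Section 10.2.1.2 for solid tumours and leaves each other disease to its own section. The endpoint names the AML and ALL criteria outright, Section 10.13 has its own unevaluable category, and Section 10.6.1 says which patients are evaluable for MIBG response. On this view Section 11 merely lacks pointers. Section 10.2.1.2 also calls evaluable-only patients evaluable in a sense, and Table 6 gives non-measurable disease an overall CR. This is probably what was meant, and a reader should not infer that the sponsor intends to disregard leukaemia remissions. But Section 11 names one section only, and both 10.2.1.2 and 13.1 keep objective response and non-target response apart. The text does not settle the matter.

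Three stronger readings are not supported:
- **That a sizeable share, such as 10 to 30%, can be taken from the background section.** Table 1 gives penetrance in bMMRD, with several rows adding to more than 100%, not the mix of enrolled patients. The figure of about one third in Section 1.1 includes lymphoma, which has target-lesion criteria. Section 1.7 lists gliomas, sarcomas, germ cell tumours and neuroblastoma as examples of hypermutation, without leukaemia.
- **That Section 13.1 makes leukaemia patients non-replaceable.** It concerns withdrawals only, and a withdrawn leukaemia patient who fits neither class would, read literally, be replaced. It is the caps that let unscored patients hold places.
- **That all these patients can score only CR.** ALL has a PR in Section 10.14, and MIBG-positive neuroblastoma has one in Table 9. The limit applies to Section 10.5 disease and, by its own rule, AML.

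**Conclusion.** The contradiction holds. Followed as written, Section 11 leaves leukaemia and evaluable-only patients without a route to be counted as responders, while early progression can count against them. The ORR is biased downward, and the patients still count toward the caps.

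The size is conditional. It rests on an assumed share, on these patients being unscored and holding capped places, on unchanged thresholds, and on a 10% null rate for Cohort B. The range in the working is illustrative, and the documents do not support saying that the stated power is in fact lost. With no such patients there is no loss; with one in the first stage, the loss is about 5 points. The definition should be corrected whatever the share proves to be.

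**What to change.** 1. In Section 11, replace the single pointer: a patient is evaluable for objective response if disease is assessable at baseline under the Section 10 criteria for that patient's diagnosis (10.4, 10.5, 10.6–10.7, 10.8–10.12, 10.13, 10.14 or 10.15). All such patients are in the denominator.
2. Align Sections 10.2.1.2 and 13.1 to the same set.
3. State whether 10/20 and 10/30 count accrued or evaluable patients.
4. Reconcile the CR plus PR decision rule with Section 10.13 (AML PR not counted) and Section 10.5 (no PR in evaluable-only disease), and say that the stated power assumes PR is attainable.

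The cost is wording in three sections, with no new data or visits. Evaluable-only and AML patients can still score only CR-type responses, so some loss of power remains after the change, in proportion to their share.
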